## **8. Description of statistical analysis**

All variables will be presented in summary tables and/or per-patients data listings (when appropriate) within treatment group and in total. Graphical presentations may be used if necessary. Descriptive statistics are defined as frequency (%) tables for qualitative variables and as number of observations, means, standard deviations, medians, Q1, Q3, and minimum and maximum values for quantitative variables. Normality of data will be determined by visual inspection of histograms. No adjustment for covariates will be made.

All statistical tests and confidence intervals will be two-sided. The level of significance will be 5%.

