7.2 SECONDARY ENDPOINTS

Secondary endpoints are:

• the total recovery rate at 12 months follow-up in the two treatment groups measured with the Sunnybrook scale (20, 21).

The Sunnybrook scale (100 is normal function and 0 is total loss of function) is another objective scale for grading the facial nerve function. It will be used as secondary outcome measure. It is validated for children, easy to perform and has been used in previous studies (20, 21). It correlates well to the House-Brackmann scale and has been shown to be useful for prediction of recovery in adult patients (21).

- the total recovery rate at 1 month follow-up as compared to the total recovery rate at 12 months follow-up, measured with Sunnybrook and House-Brackmann scale (prediction) (20, 21).
- quality of daily life at 1 and 12 months follow-up measured with the Facial Clinimetric Evaluation (FaCE) scale and the Facial Disability Index (FDI) and at the 12 months measured with the Synkinesis Assessment Questionnaire (SAQ) (22, 23).
- number of Adverse Events possibly or probably related to the study drug during the 12 months follow-up.

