8.2 STUDY ASSESSMENTS AND PROCEDURES

A Principal Investigator (a pediatrician) at each study center will be responsible for clinical care of the patients.

The Principal Investigator (a pediatrician) or a co-Investigator (an Ear-Nose-Throat specialist) will be responsible for performing the objective evaluation of the facial nerve function on admission (or one day after) and at the follow-up visits 1 month and 12-months.

The Principal- and co-Investigators at each study center will be thoroughly informed how to assess the House-Brackmann and Sunnybrook scales in order to minimize inter-rater differences.

Study nurses will take care of parts of the study work, such as performing the one and two weeks telephone calls, collecting questionnaires from the child/parents/guardians, collecting and entering data in the CRFs and being the main contact person for the monitor.

Screening/Baseline visit

Children and their parents/guardians visiting the hospital for the child's acute facial nerve palsy will be informed about the study and eligibility criteria will be checked. If the child and the parents/guardians accept to participate in the study, an informed consent (ICF) will be signed by both parents/guardians. If only one parent/guardian is present at the visit, the other parent/guardian will be contacted by telephone, informed about the study, given the chance to ask questions and sent an ICF by email. The signed ICF will then be sent back by e-mail, or as a photocopy on the

mobile phone, to the investigator and saved in the Investigators file until the original ICF is returned.

Data about demographics, medical history, concomitant medication, physical examination including blood pressure will be collected. Blood sample for white and red blood cell count, CRP, electrolytes and glucose as well as investigation of the spinal fluid will be performed as part of normal clinical routine. The NeBoP score (a clinical neuroborreliosis prediction test), as used in routine, will be assessed on all children for early prediction of diagnosis associated to *Borrelia* infection (24).

Grading of the facial nerve palsy by using the House-Brackmann and Sunnybrook scales will be performed either by a pediatrician or an ear-nose-throat specialist (the principal or co-investigator).

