11 ASSESSMENT OF EFFICACY

11.1 INVESTIGATOR'S ASSESSMENTS

The Investigators will perform evaluation using the House-Brackmann and Sunnybrook grading scales for facial nerve palsy at the three study visits (screening/baseline, 1 month, 12 months). Education for the study, including written instructions on how to perform the evaluation will be given to the investigators before study start.

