## 6. Study design

The FACE study is a randomized double-blind, placebo-controlled, multicenter trial. The study is a randomized two armed intervention study with several well-defined clinical outcome measures with a superiority hypothesis testing in favor for the intervention (prednisolone).

Children with acute facial nerve palsy (idiopathic or *Borrelia*-associated) will be recruited at 17 study centers during 2019-2023 and followed during 12 months. Inclusion and exclusion criteria are set.

The Principal Investigator (a pediatrician) or a co-Investigator (an Ear-Nose-Throat specialist) will be responsible for performing the objective evaluation of the facial nerve function on admission (or one day after) and at the follow-up visits 1 month and 12-months.

Study nurses will take care of parts of the study work, such as performing the one and two weeks telephone calls, collecting questionnaires from the child/parents/guardians, collecting and entering data in the CRFs and being the main contact person for the monitor.

Participants are randomly assigned to prednisolone or placebo. Content in bottles with study drug are blinded and coded after a randomization list in variable blocks without stratification. Bottles with study drug has been distributed to each study center.

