### 8.5. Primary efficacy analyses

Efficacy of cortisone treatment versus placebo will be compared between intervention group and control group at 12-months follow-up, with the outcome measured with House-Brackmann. Recovery will be defined as HB=1. Comparisons between dichotomous variables (i.e. recovered/not recovered) will be performed between groups using Chi2 (or Fisher's exact test) with risk estimate and 95% confidence interval. Mann-Whitney U-test will be used when comparing score medians for the House-Brackmann grading scale.

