### 8.8. Handling of Missing Data

Missing values where the patients have been completely recovered at the last visit will be imputed with the method of last observation carried forward (LOCF).

Other missing values where patients have not been recovered and did not complete follow-up clinic visits will be imputed using worst case last observation carried forward.

The LOCF method will be used for the primary analysis only. For secondary analyses, the complete case analysis will be applied.

In case of incomplete start dates and end dates of adverse events, the "worst case" date will be used. For example, if "December 2020" is recorded as the time of start or end of an adverse event, December 1, 2020 and December 31, 2020, will be used as start- and end-date, respectively.

The last pre-administration observation will be used as the baseline value for calculating post-administration changes from baseline.

For other variables, missing data will result in a reduced sample size for that parameter. A patient who withdraws prior to the last planned observation will be included in the analysis up to the time of discontinuation.

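### SAP 8 rules out covariate adjustment although baseline severity is scheduled for every child: a supportive severity-adjusted risk difference and one aetiology contrast would be cheap additions to a sound primary test

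*SAP*

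**What the plan says.** - **Covariates.** The general conventions at the head of SAP 8 include the sentence "No adjustment for covariates will be made", with no stated exception.
- **Primary analysis.** SAP 8.5 words the comparison as "i.e. recovered/not recovered) will be performed between groups using Chi2", or Fisher's exact test, with a risk estimate and 95% interval. The scale of that estimate is not named.
- **Randomisation.** SAP 6: study drug is "coded after a randomization list in variable blocks without stratification".
- **Baseline severity.** Protocol 11.1 has investigators apply the "House-Brackmann and Sunnybrook grading scales for facial nerve palsy at the three study visits (screening/baseline, 1 month, 12 months"). The visit schedules in Protocol 8.3 and SAP Table 1 agree. Of Sunnybrook, Protocol 7.2 says it "has been shown to be useful for prediction of recovery in adult patients". No figure is given, and nothing is said about prognosis in children.
- **Timing.** Protocol 8.2 places the "objective evaluation of the facial nerve function on admission (or one day after"). SAP 8.8 says "The last pre-administration observation will be used as the baseline value".
- **Missing data.** SAP 8.8: "The LOCF method will be used for the primary analysis only. For secondary analyses, the complete case analysis will be applied".
- **Other regressions.** SAP 8.6.1 combines the 1-month score with baseline variables. SAP 8.9 lists diagnosis, treatment, age group and gender. Protocol 13.2 relates recovery to baseline data.
- **Aetiology.** SAP 8.9 compares recovery between arms in idiopathic or *Borrelia*-associated palsy. Its text names no interaction. The output shells in Appendix 1 are cited but were not available.

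**The concern.** Severity at presentation is the natural candidate for a prognostic covariate. The trial schedules it for every child and leaves its balance to chance. If it predicts recovery, an adjusted risk difference is more precise than the crude one. It also gives a pre-specified answer if the arms happen to differ in severity. None of the planned regressions is described as supplying that. The models in 8.6.1 contain the 1-month score, which is measured after randomisation and may itself be affected by treatment, so they cannot stand in for a baseline-adjusted effect.

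The aetiology comparison raises a separate issue. Two within-group results with no contrast between them invite the reader to compare significance. The sponsor intends the results to support guidelines (Protocol 5.1), so a mistaken conclusion that the drug works in only one aetiology would matter.

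**Working it through.** **1. The plan's own figure.** Inputs from SAP 9: 80% v 90%, two-sided 5%, 80% power, 430 evaluable, 500 enrolled. Fisher's exact power by full enumeration is 0.803 at 215 per arm (0.792 at 210), so 430 reproduces. The normal formula with continuity correction gives 219 per arm, 438 in total. Exact power without adjustment:

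| N | Fisher | Chi-square |
|---|---|---|
| 430 | 0.803 | 0.836 |
| 450 (500 less 10%) | 0.821 | 0.854 |
| 500 | 0.863 | 0.887 |

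**2. Unadjusted interval.** Half-width = 1.96 × √(0.80×0.20/n + 0.90×0.10/n).
- n = 250 per arm: 1.96 × 0.0316 = 6.2 points.
- n = 225 per arm: 1.96 × 0.0333 = 6.5 points.

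**3. Adjusted interval.** The prognostic strength is assumed. Take a standard normal score in a logistic outcome model, with marginal recovery fixed at 80% and 90%. With p0 and p1 the individual recovery probabilities under placebo and prednisolone, the large-sample variance ratio for a standardised risk difference is

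[2·E{p0(1−p0)} + 2·E{p1(1−p1)} + Var(p1−p0)] / [2(0.16+0.09)].

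The half-width is the unadjusted value times the square root of this ratio.

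| Assumed AUC | Variance ratio | N = 500 | N = 450, complete cases |
|---|---|---|---|
| 0.50 | 1.00 | 6.2 | 6.5 |
| 0.64 | 0.97 | 6.1 | 6.4 |
| 0.73 | 0.90 | 5.9 | 6.2 |
| 0.79 (odds ratio about 3.5 per SD) | 0.84 | 5.7 | 6.0 |

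At N = 500 the interval is 0% to about 8% narrower: 1 − √0.84 = 0.08. A simulation at N = 500 (8,000 trials per setting) gave ratios of 1.003, 0.969, 0.920 and 0.844, which lead to the same half-widths at this rounding. Three further results:
- At AUC 0.79, with 25% or 50% of baseline scores missing and mean-filled, the ratio rises to 0.889 or 0.933. The half-widths become 6.2 × √0.889 = 5.8 and 6.2 × √0.933 = 6.0.
- With no true effect (AUC 0.73, N = 500, 25% missing, 16,000 trials), rejection was 0.048 unadjusted and 0.050 adjusted.
- The last column shows why the analysis set matters. Under the complete-case rule for secondary analyses, most of the gain over the 6.2 of the primary analysis disappears.

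**4. Aetiology.** Protocol 5 gives 65% *Borrelia*-associated and 35% idiopathic as background. It is used here as an assumed enrolment split, with 80% v 90% in both groups.
- N = 500: power within groups is 0.721 and 0.458. Exactly one significant: 0.721×0.542 + 0.458×0.279 = 0.52.
- N = 450: 0.679×0.568 + 0.432×0.321 = 0.52.
- Splits from 50/50 to 80/20 give 48% to 62%.
- The contrast of the two risk differences is significant in about 5% of such trials. Its standard error at N = 500 is √(0.25/162.5 + 0.25/87.5) = 6.6 points, a half-width of 13.0 (13.7 at N = 450).
- Its power for a 10-point difference in effects is 26% to 31% at N = 450 and 28% to 34% at N = 500, depending on which group gains and by how much.

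**The case against.** An unadjusted chi-square or Fisher test under unstratified randomisation is a legitimate pre-specified choice, and it matches Protocol 13.2. A supportive model leaves the main interval and the trial's power where they were, and its benefit rests on a prognostic strength that no document gives. The top of the range needs an odds ratio of about 3.5 per SD. All of this stands, and it is why the point is an improvement only.

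The N = 500 figures also assume that outcomes imputed under SAP 8.8 keep 80% v 90%. Suppose instead that 10% are carried forward at 40% recovery in both arms. The rates become 0.9×80 + 0.1×40 = 76% and 0.9×90 + 0.1×40 = 85%, and power is about 72%. At 70% recovery it is about 78%. That caution bears on the adjusted and unadjusted analyses alike.

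A reader might infer more than the documents support:
- *That the primary test is invalid or undersized without adjustment.* It is neither on the plan's own assumptions; 430 reproduces.
- *That SAP 8 contradicts 8.6.1 and 8.9.* Those models serve prediction. The sentence in 8 does not say that it concerns only the treatment comparison, which is a matter of wording and scope.
- *That the SAP will judge the aetiologies by which p-value is significant.* It does not say so; the 52% describes what readers might do.
- *That no interaction is planned anywhere.* Appendix 1 could contain one and could not be checked.

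**Conclusion.** The point holds as a low-cost improvement, not an error. The supplied text provides no treatment effect adjusted for baseline severity. Adding one would give a second, pre-specified estimate with a 95% interval 0% to about 8% narrower at N = 500. This rests on an assumed AUC of 0.50 to 0.79, on imputed outcomes that keep 80% v 90%, and on use of the primary analysis set. The gain may be nil.

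The aetiology contrast would be descriptive, because its power is low. Its value is to give readers an estimate and an interval in place of two separate p-values. The 52% assumes a 65/35 split and equal placebo recovery in both groups.

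**What to change.** Settle these before unblinding.

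1. **SAP 8.** Limit the sentence: *The primary chi-square/Fisher comparison in 8.5 is not adjusted for covariates; this does not apply to the supportive model in 8.5 or to the regressions in 8.6.1 and 8.9.*
2. **SAP 8.5.** State that the primary risk estimate is a risk difference, so that the two analyses can be compared. Add one supportive logistic model for House-Brackmann grade 1 at 12 months, with treatment, pre-dose baseline Sunnybrook (continuous) and age (continuous). Use the ITT set and outcome imputation of the primary analysis, and report a standardised risk difference with 95% CI. Replace a missing or post-dose baseline score by the mean over both arms and include a missing indicator.
3. **SAP 8.8.** Name this model as an exception to the complete-case rule.
4. **SAP 8.9.** Report the risk difference with 95% CI in each aetiology, and the difference between them with 95% CI. Label it exploratory, note the low power, and state that a non-significant contrast does not show equal effects. Naming the scale matters: with assumed placebo recovery of 85% and 75% in the two groups, a uniform 10-point benefit is real heterogeneity on the logit scale, and a logit interaction would be significant 9% to 16% of the time.

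The cost is a few SAP sentences, one model and one contrast. The primary test and the protocol stay as they are, and no assessment is added. SAP 12 lists no derived aetiology variable and the CRFs were not available, so check that aetiology and the time of grading relative to the first dose are recorded.

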### **8.1. Study conduct and Subject/Patient disposition**

The number of patients included in the study will be presented together with the number of patients by visit (1 month, 12 months). The numbers withdrawn in total and for each pre-defined withdrawal reason, and the allocation of patients to each analysis population group will be presented in the table. Number of patients will be presented by treatment and in total.

### **8.2. Baseline Characteristics and Treatment Group Comparability**

Demographics and baseline characteristics such as age, sex, weight, blood pressure, NeBoP test etc. will be summarized by treatment group and in total.

Continuous variables such as Sunnybrook-scale will be summarized by number of observations (n), mean, standard deviation (SD), median, minimum (min) and maximum (max). Categorical variables will be summarized in frequency tables (presenting frequencies and proportions). Medical history will be presented in a table and, if appropriate listed as a per-patient data listing. Adverse Events that occur before first treatment will be reported separately as baseline event.

### 8.3. Treatment Administration/Compliance

The intervention is treatment with either prednisolone (capsule Prednisolone 5 mg), 1 mg/kg once daily in 10 days or control treatment (capsule placebo) once daily in 10 days. The number of capsules is based on the child's weight and presented in the table below:

Child's weight /kg	Number of capsules/day	Total number of capsules
5 - 9.9	2	20
10 - 14.9	3	30
15 - 19.9	4	40
20 - 24.9	5	50
25 - 29.9	6	60
30 - 34.9	7	70
35 - 39.9	8	80
40 - 44.9	9	90
>45	10	100

Capsule Prednisolon 5 mg (APL), dosage 1 mg/kg (max 50 mg) once daily for 10 days according to pre-calculated weight. All bottles include 100 capsules.

Compliance for the 10 day period:

Compliance (0-100%) = (Number of tablets actually taken x 100)/total number of capsules

Patients with treatment compliance less than 70% will be excluded from the PP analysis. Patients with 0% compliance will be excluded from ITT analysis.

### 8.4. Concomitant medications

Children with *Borrelia* associated acute facial nerve palsy will receive antibiotic treatment according to national guidelines.

All other concomitant medications permitted in the study will be presented in per-patient data listings and in a table by treatment group and in total. Data registered are generic/trade name, dosage, start and end date of the medication, and indication.

### 8.5. Primary efficacy analyses

Efficacy of cortisone treatment versus placebo will be compared between intervention group and control group at 12-months follow-up, with the outcome measured with House-Brackmann. Recovery will be defined as HB=1. Comparisons between dichotomous variables (i.e. recovered/not recovered) will be performed between groups using Chi2 (or Fisher's exact test) with risk estimate and 95% confidence interval. Mann-Whitney U-test will be used when comparing score medians for the House-Brackmann grading scale.

## 8.6. Secondary efficacy analyses

Efficacy of cortisone treatment versus placebo will be compared between intervention group and control group at 12-months follow-up, secondarily with the outcome measured with Sunnybrook scale. Recovery will be defined as SB=100. Comparisons between dichotomous variables (i.e. recovered/not recovered) will be performed between groups using Chi2 (or Fisher's exact test) with risk estimate and 95% confidence interval. Mann-Whitney U-test will be used when comparing score medians for the Sunnybrook grading scale or other continuous variables.

Results for continuous variables will be given as median values with interquartile range (IQR; 25th to 75th percentiles) and dichotomous data (i.e. full recovery/not full recover) as proportions with 95% confidence interval using the normal approximation approach.

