### 8.9. Subgroup analysis

Recovery (at 12 months) between treatment groups will be analysed in the subgroup:  
-children with idiopathic facial nerve palsy or *Borrelia* associated facial nerve palsy

To predict recovery at 12 months follow-up logistic regression analysis will be used by following subgroups:

- diagnosis (*Borrelia* associated/Not *Borrelia* associated)
- treatment (Prenisolone/Placebo)
- age group (1-5, 6-10, 11-14, 15-18)
- gender (Girls/Boys)

Presentation of the results is described in section 8.6.1

Subgroup analysis for comparison between Placebo and Prednisolone at 1 and 12 month for QoL variables and HB/SB scales will be performed (see Appendix 1 table 7)

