## 9. Determination of sample size

Sample size for the FACE study is calculated on the primary outcome (i.e. number (%)) of patients with total recover of the facial nerve palsy in each intervention group, measured by House-Brackmann grade 1, at 12 months follow-up). An 10% difference of the total recovery rate between groups (80% in placebo group versus 90% in prednisolone group) is an estimation from earlier non-RCT studies, interviews with children/parents (unpublished data) and a test of two independent proportions for estimation of the minimal relevant clinical improvement (MRC). To show that such a difference is significant ( $p < 0.05$ , two-sided test) with 80 % power, a total of 430 patients are needed. However, due to the uncertainty in the assumptions and to that a portion (10%) of patients not taking part of the study follow-up, 500 patients will be included in the FACE study (250 in each group).

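### SAP 8.6 prescribes normal-approximation intervals for recovery proportions expected near 90%; they under-cover slightly in the full arms and more in small subgroups, and Wilson limits would correct this at almost no cost

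*SAP*

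**What the plan says.** SAP section 8.6 (Secondary efficacy analyses) states that full recovery, yes or no, is given "as proportions with 95% confidence interval using the normal approximation approach". Neither that section, nor the general rules in section 8, nor the subgroup section 8.9 offers another method for small groups or for proportions close to 100%.

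The rates to expect come from SAP section 9: "80% in placebo group versus 90% in prednisolone group", with 250 children per arm and an allowance for "a portion (10%) of patients not taking part of the study follow-up". Section 8.8 imputes missing values for the primary analysis, but "For secondary analyses, the complete case analysis will be applied". Section 8.9 compares 12-month recovery between arms in "children with idiopathic facial nerve palsy or *Borrelia* associated facial nerve palsy"; it gives no subgroup sizes and no interval method.

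The comparison between arms in sections 8.5 and 8.6 uses a chi-squared or Fisher test and a risk estimate with a 95% interval of unnamed type. The normal-approximation sentence therefore governs the reported proportions and not the test.

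**The concern.** The Wald interval is centred on the observed proportion and takes its width from the observed variance. When the true proportion is near 1, samples with few non-recovered children give both a high estimate and a short interval. The misses then fall mostly on one side, with the interval lying above the truth. In small groups the upper limit can pass 100%, and with no unrecovered child the interval collapses to the single point 100%.

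Recovery rates by arm, overall and by cause, are what clinicians and families will read most directly. The lower limit is the figure they would take as the least recovery to expect, and it is the limit that errs in the optimistic direction.

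**Working it through.** **Inputs**
- Confidence level 95%, two-sided (SAP section 8): z = 1.96, z² = 3.84.
- Recovery rates 80% and 90% (SAP section 9). The range 0.87 to 0.93 is used around the higher rate so that no single value decides the result.
- Children per arm: 250 randomised; 250 × 0.90 = 225 after the stated loss; 215 is half of the 430 needed.
- Idiopathic subgroup: 35% (Protocol section 5, a background figure and so an assumption here). 0.35 × 225 ≈ 79 and 0.35 × 250 ≈ 88 per arm.
- A cell of 56 per arm: 225 / 4, if the four age bands of SAP section 8.9 were equal (assumption).

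**The plan's own figure.** SAP section 9 says "80 % power, a total of 430 patients are needed". Exact power of Fisher's test for 80% v 90% is 80.1% at 214 per arm and 80.3% at 215 per arm, so 430 is reproduced. 430 / 0.90 = 478, which is below the 500 planned.

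**Formulas.** With x recovered of n and q = x/n:
- Wald: q ± z √(q(1 − q)/n).
- Wilson: centre (q + z²/2n) / (1 + z²/n), half-width [z / (1 + z²/n)] √(q(1 − q)/n + z²/4n²).
- Exact coverage at true rate p: the sum of the binomial probabilities of every x whose interval contains p.

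**Coverage at p = 0.90**

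| n | Wald | Wilson | Wald wholly above p | Wald wholly below p | Wald upper limit > 100% |
|---|---|---|---|---|---|
| 250 | 93.2% | 95.6% | 5.1% | 1.7% | < 0.01% |
| 225 | 92.9% | 95.6% | 5.4% | 1.7% | < 0.01% |
| 88 | 93.4% | 95.3% | 5.3% | 1.3% | 2.0% |
| 79 | 89.5% | 96.4% | 9.4% | 1.1% | 3.8% |
| 56 | 92.0% | 95.9% | 7.2% | 0.8% | 17.3% |

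At p = 0.80, Wald covers 94.2% at n = 225 and 95.0% at n = 250.

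**Averages.** Coverage moves in a sawtooth as n changes: at p = 0.90, n = 78 gives 94.9% and n = 79 gives 89.5%. The averages over p = 0.87 to 0.93 are the fairer summary:
- 215 to 250 per arm: Wald 94.1%, Wilson 95.1%.
- 79 to 88 per arm: Wald about 92.6%, with single values from about 88% to 95%; Wilson 95.2%.

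**Width and position.** 203/225 gives Wald 86.3% to 94.1% (width 7.76 points) and Wilson 85.6% to 93.5% (width 7.81 points). The widths are almost equal. Wald sits higher by 0.70 points at the lower limit and 0.65 at the upper. For 225/250 the limits are 86.3% to 93.7% and 85.7% to 93.1%, a shift of about 0.6 points.

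**When the upper limit passes 100%.** Let u be the number not recovered. The condition q + z √(q(1 − q)/n) > 1 reduces to 0 < u < 3.84 / (1 + 3.84/n). For n of at least 14 this means u = 1, 2 or 3. At p = 0.90 the expected u is 22.5 when n = 225, so this practically never happens there. It is 7.9 at n = 79 and 5.6 at n = 56, which gives the last column of the table.

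**The case against.** The strongest reply is that the normal approximation is conventional with 225 to 250 children and more than 20 unrecovered per arm, and that replacing it is largely a matter of taste. Much of this stands. In the full arms the average shortfall is about one point, at 80% recovery it is close to nil, and a shift of 0.6 to 0.7 points would not change how the trial is read. At some sample sizes Wald even does better: at p = 0.90 and n = 222 it covers 95.0% against 94.4% for Wilson.

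A reader might go further than the documents allow in four ways:
- **That the main results are covered well below 95%, with error bars too narrow.** The full-arm averages and widths above do not support this. Single low values such as 89.5% at n = 79 are troughs of the sawtooth.
- **That limits above 100% will be common.** At a 95% recovery rate and n = 79 the share would be 42%, but 95% is not a planning rate. At 90% it is 3.8%.
- **That the subgroup sizes are planned.** They are not. The 65/35 split is epidemiological background, the equal age bands are assumed, and the SAP does not say outright that the section 8.6 method applies to the subgroup tables. It does, however, name no other method for a proportion.
- **That the interval for the difference between arms is faulty.** Its type is not named. A Wald interval for 90% v 80% would cover 95.0% at 225 per arm and 94.7% at 79 per arm.

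What the reply does not answer is the direction of the error. Even in the full prednisolone arm at n = 225, the interval lies wholly above the true rate about twice as often as it should.

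**Conclusion.** The point holds as a small, one-sided calibration fault in descriptive intervals. Near 90% recovery, coverage averages about 94% in the full arms and about 92.6% with 79 to 88 children per arm, against about 95% for Wilson in both. Impossible limits are a matter for small cells only. The subgroup figures depend on the assumed split by cause and on the realised n, so they should be read as ranges.

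No primary test, p-value or sample size is affected. The size n = 225 applies most directly to the complete-case Sunnybrook result; because missing House-Brackmann outcomes are imputed for the primary analysis, its n should be nearer 250, where the picture is almost the same (93.2% at p = 0.90). The change is worth making because it is specific, better calibrated and essentially free.

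**What to change.** In SAP section 8.6, replace the normal-approximation wording with Wilson score 95% intervals for single recovery proportions. State that this applies to House-Brackmann and Sunnybrook recovery, overall and in the subgroups of section 8.9. The cost is one phrase in the SAP; the method is a standard option in SAS and R, both listed in SAP section 14, and needs no change to data, conduct or sample size. It should be made before database lock, by which point Protocol section 13.2 requires the SAP to be final, so that the method is not chosen after results are seen.

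Naming the interval type for the risk estimate between arms in sections 8.5 and 8.6 would add clarity, but it is optional, since no defect is shown there.
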